shoulder arthroscopy who receive post-operative CBD and a placebo group. Patients will be asked on postoperative Day 1, 2, 7, and 14 to rate their pain according to the VAS scale. Additionally, opioid consumption, CBD consumption, as well as patient satisfaction will be measured. Patients will be asked in the post-trial period to fill out a questionnaire pertaining to 1-year outcomes. The questionnaire will be in the form of a single online survey including ASES score, VAS score, KJOC Shoulder score, and SANE score.

Rationale for multi-center study:

The second site is essential for this project, for both recruitment and logistical purposes. While NYULOH does have high-volume, a large proportion of these patients will be ineligible due to the exclusion criteria and will not want to participate given that this is a randomized, controlled, double blinded study. Additionally, the second site PI was absolutely instrumental in the conceptualization and the design of this study, as well as securing the necessary funding for it happen. This study would not be feasible without their collaboration. Additionally, the second site PI has an academic appointment here at NYU Langone, and is instrumental in the education of the trainees here at our institution

Primary Objective

The primary objective of the study is to determine if there are any differences in post-operative pain between patients receiving CBD after shoulder arthroscopy compared to patients who do not receive it.

Secondary Objective

Secondary objective of the study is to determine if there are any differences in patient satisfaction, the incidence of opioid induced nausea, and the numbers of opioids and CBD/placebo ODTs consumed by the two patient cohorts.

II. CHARACTERISTICS OF THE RESEARCH POPULATION

Number of Subjects

We will aim to enroll a total of 100 subjects (50 per cohort) as determined by the priori sample size calculator.

Gender of Subjects

Men and women will be included in this study.

Age of Subjects

Subjects included study will be aged 18-75 years, inclusive.

Racial and Ethnic Origin

There are no enrollment restrictions based on race or ethnic origin.

Inclusion Criteria

Patients will be screened for eligibility using the following criteria. All study subjects must meet the following inclusion criteria:

- Patients undergoing an arthroscopic shoulder procedure (rotator cuff repair, decompression, labrum repair)
- Patients ages 18-75, inclusive

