| CYP1A2 Substrates | Acetominaphen, Amitriptyline, Clomipramine, Clozapine, Cyclobenzaprine, Doxepin, Duloxetine, estradiol, Fluvoxamine, Haloperidol, Imipramine n-deme, mexiletine, nabumetone, Napqi, Naproxen, Olanzapine, Ondansetron, Phenacetin, Perfenidone, Propranolol, Riluzole, Ropivacaaine, Rucaparib, Tacrine, Theophylline, Tizanidine, Triamterene, Verapamil, Warfarin, Zileuton |
| CYP2B6 Substrates | Artemisinin, Bupropion, Cyclophosphamide, Efavirenz, Ifosfamide, Ketamine, Meperidine, Methadone, Nevirapine, Propafol, Selegine, Sorafenib, Tramadol, Velpatasvir |
| CYP2C8 Substrates | Amiodaquine, Cerivastatin, Paclitaxel, Repaglinide, Selexipag, Sorafenib, Torsemide |
| CYP2C9 Substrates | Amitriptyline, Capecitabine, Celecoxib, Clopidogrel, Diclofenac, Doxepin, Fluoxetine, Fluvoxamine, Glibenclamide, Glimepiride, Glipizide, Glyburide, Ibuprofen, Irbesartan, Lesinurad, Lornoxicam, Meloxicam, Nateglinide, Phenytoin-4-oh2, Piroxicam, Rosiglitazone, S-naproxen-nor, S-warfarin1, Suprofen, Tamoxifen, Tolbutamide, Tolbutamide1, Torsemide, Valproic Acid, Venlafaxine, Voriconazole, Zakirlukast |
| CYP2C19 Substrates | Amitriptyline, Atomoxetine, Brivaracetam, Carisoprodol, Chloramphenicol, Citaprolam, Clomipramine, Clopidogrel, Cyclophosphamide, Diazepam-nor, Doxepin, Escitalopram, Esomeprazole, Flibanserin, Hexobarbital, Imipramine-n-deme, Indomethacin, Labetalol, Lansoprazole, Moclobemide, Nelfinavir, Nilutamide, Omeprazole, Pantoprazole, Phenobarbitone, Phenytoin(o), Primidone, Progesterone, Proguanil, Propranolol, r-Methobarbital, r-Warfarin, s-Mephotoxin, Suvorexant, Teniposide, Venlafaxine, Vorconizole |

Vulnerable Subjects

We do not intend to enroll vulnerable subjects.

Subject withdrawal criteria.

Patients are free to withdraw of their own volition at any time from the study before or after surgery.

A subject may be withdrawn from the study at any time if the Investigator determines that an illness, injury, complication or adverse event requires immediate study removal, whether or not considered by the Investigator to be related to the study drug.

Subjects found to have elevated liver transaminase and/or bilirubin levels on Day 2, or Day 7 will be removed from the study.

III. METHODS AND PROCEDURES

Methods and Procedures

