Information to be recorded pre-operatively includes age, sex, height, weight, BMI, and American Society of Anesthesiology (ASA) classification. As well as baseline levels of complete blood count (CBC), chemistry profile, liver enzymes, gamma glutamate transferase (GGT), electrocardiogram, urine analysis, 12-panel urine drug test, and a urine pregnancy test.

Intra-operative information will also be recorded, including operative time, procedure, number of anchors, and complications. Patients will subsequently be stratified in different subgroups based on the procedure performed.

Pain severity scores at rest will be assessed by use of a visual analog scale (VAS; 0 = no pain, 10 = worst pain imaginable) at 6, 24, and 48 hours as well as 7 days and 14 days after surgery.

Patients will record their satisfaction with their management, on a 0-10 scale, 24 hours, 2 days and 7 days, and 14 days after surgery.

Additionally, any nausea experienced by the patients will be recorded by use of a VAS (0 = no nausea, 10 = worst nausea imaginable) at 2 days, 7 days and 14 days after surgery.

Percocet consumption will be recorded at 24 hours, 2 days and 7 days, and 14 days after surgery. Additionally, subjects will be asked to record the dates and times of CBD consumption.

Liver function tests, consisting of the standard hepatic panel, and including serum transaminase and bilirubin levels will be administered for study purposes on Day 7 and Day 14 after surgery.

Incidence of CBD-related side effects will be noted. Time to discharge from the post-anesthesia care unit (PACU) and time to discharge from the hospital will be recorded. Patients will be in the study a duration of 14 days and will be asked to fill out one online survey at the 1-year mark to determine the long-term effects that may be associated with using CBD.

In order to maintain the blinding, all data, including pain severity scores, side effects, opioid and CBD consumption, will be collected by the resident physician or physician assistant. However, if needed, in the event of an emergency or SAE, the unblinded surgeon responsible for randomization will be able to confirm whether a subject has been assigned to receive CBD or placebo.

| Study Time Points | |
|------------------------|---|

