To compare primary outcomes (VAS score), a T-Test test will be performed, with a p-value of 0.05 set to determine statistical significance. Testing will be performed to determine whether sample distribution is normal; if not, non-parametric testing will be performed. Patients who do not complete at least 80% of follow-up visits will be considered lost to follow-up and will not be included in the analysis.

Analysis of the Secondary Endpoint(s)

To compare secondary outcomes (opioid use, satisfaction), complication rates), a T-Test will be performed, with a p-value of 0.05 set to determine statistical significance. For categorical variables, a Fisher's exact test will be performed. Testing will be performed to determine whether sample distribution is normal; if not, non-parametric testing will be performed. Patients who do not complete at least 80% of follow-up visits will be considered lost to follow-up and will not be included in the analysis.

Data and Safety Monitoring Plan

Data monitoring will be done by [name], the principal investigator will oversee the conduct of the study. He will review enrollment, accumulated study data, including pain VAS scores, Percocet consumption VAS scores, liver function test results, adverse events, protocol deviations, study compliance and data accuracy quarterly.

He will monitor whether or not:

1. Collection and storage of patient data was performed in a sensitive and secure manner, as defined in the informed consent form and protocol, ensuring information is stored on REDCap.
2. All study activities were conducted with primary emphasis on patient care and wellbeing, ensuring the patients are not in discomfort and have an abnormally high VAS following the surgery.
3. If there were any adverse events, and if so were addressed appropriately and per protocol
4. The risk/benefit to patients has remained the same throughout the course of the study.

The study will be stopped if there are unexpected severe adverse events in more than one patient. Adverse Events (AEs) will be defined as negative reactions to the CBD treatment. We will submit summaries of data and safety monitoring to the IRB annually. De-identified primary and secondary outcome data will be shared by the participating site PI quarterly, and they will notify the host site PI ([name]) upon each enrolled patient.

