Planned safety monitoring during the duration of the study will include monitoring for liver function, laboratory abnormalities and suicidality assessments throughout the study and for follow-up visits. Liver function tests, including serum transaminase and bilirubin, will be obtained on Day 2, Day 7, and Day 14. Elevated liver transaminase and bilirubin levels will be grounds for immediate removal from the study. C-SSRS will be assessed at baseline, Day 7, and Day 14 by the surgeon. Although CBD does not increase risk of suicidal ideation and behavior, this is being done in accordance with FDA recommendation for clinical trials involving drugs with CNS activity. If subjects are found to pose a risk to themselves, standard institutional procedures will be followed to refer subjects for appropriate care, including emergency care if needed.

The maximum CBD dose given to any subject will be less than 2mg/kg/day, well below levels associated with any hepatic risk (Iffland & Grotenherman, 2017).

The use of cannabidiol (CBD) in pain reduction and opioid use after shoulder arthroscopy. A Double-Blind, Randomized Control Study

Version 06/28/2022

CBD was not deemed to increase the severity of Percocet's opioid toxicities, as they act on different pathways. There is a potential for CBD to work in the same C450 cytochrome pathway as the acetaminophen, and thus no additional acetaminophen is to be prescribed outside of this, which is well below the maximum prescribing threshold of 4g per day.

The patients will stay in the recovery unit until cleared for discharge by an anesthesiologist. They will be prohibited from driving or operating a motor vehicle for 2 hours following their first dose of the study drug.

Patients will be educated on the importance of keeping the study drug in a safe place at all times and ensure it is not accessible to anyone other than themselves.

Additionally, all patients will be de-identified and given a code. Information linking the patient codes to the participants' names and medical record numbers will be stored in a secure location separate from the medical information. Access to the information linking the linkage codes with participant identifiers shall be restricted.

Potential Benefits to the Subjects

Patients may experience less pain post-operatively, and may require less narcotics use, which has a steeper side-effect profile. However, these benefits cannot be guaranteed.

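### The 80% visit rule has no exception for complication rates, so patients removed early because of a harm can drop out of the by-arm comparison of harms

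*Combined protocol and SAP*

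**What the plan says.** Under Analysis of the Secondary Endpoint(s) the plan writes: "To compare secondary outcomes (opioid use, satisfaction), complication rates), a T-Test will be performed". It gives Fisher's exact test for categorical variables, then says that patients who "do not complete at least 80% of follow-up visits will be considered lost to follow-up and will not be included" in the analysis. No safety outcome is exempted, and neither complication rates nor follow-up visits is defined.

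Three provisions take patients out of the study for a harm:
- Subject withdrawal criteria: "Subjects found to have elevated liver transaminase and/or bilirubin levels on Day 2, or Day 7 will be removed from the study".
- The same section allows withdrawal at any time "if the Investigator determines that an illness, injury, complication or adverse event requires immediate study removal".
- Protection against Risks: "Elevated liver transaminase and bilirubin levels will be grounds for immediate removal from the study".

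On what is recorded, Methods and Procedures says: "Intra-operative information will also be recorded, including operative time, procedure, number of anchors, and complications". It is the only list of recorded data that names complications. Adverse events are collected separately, reviewed quarterly and followed to resolution (Data and Safety Monitoring Plan; Adverse Event Reporting). The Secondary Objective compares satisfaction, opioid-induced nausea and tablet counts between cohorts.

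**The concern.** A completeness rule written for efficacy data is applied, in the same paragraph, to an outcome that may be a safety outcome. The removal rules make early departure a consequence of harm. Together they can make inclusion in the harm comparison depend on whether the patient was harmed.

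The liver case matters most. The Risk section lists hepatic toxicity as a rare side effect of CBD. Both arms also take acetaminophen as part of Percocet, and Protection against Risks notes that CBD may share its metabolic pathway. A raised liver test on CBD therefore needs the placebo arm to be interpreted. If early cases leave both numerator and denominator, the absolute rates fall. If CBD causes more early removals than placebo, the risk difference shrinks too.

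**Working it through.** The plan gives no figure for this point; its sample size calculation concerns pain scores only. The check is therefore a count of visits, followed by an illustration on assumed events.

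**Step 1: what has to hold.**
- *Assumption A:* complication rates includes post-operative events. For it: the withdrawal criteria name a complication as a reason to leave the study, and Study Design compares patients undergoing "shoulder arthroscopy who receive post-operative CBD and a placebo group", so intra-operative complications could not show an effect of CBD. Against it: complications are listed as recorded data only intra-operatively.
- *Assumption B:* removal from the study ends the visits that count. This is the plain reading, but the documents do not say so.

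**Step 2: share of visits completed.** The schedule comes from Methods and Procedures and the Study Time Points table. Share = visits up to and including the day of removal / all visits counted. A patient is kept if the share is at least 80%.

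| In-study count | Removed Day 2 | Removed Day 7 | Removed Day 14 |
|---|---|---|---|
| Days 1, 2, 7, 14 | 2/4 = 50%, out | 3/4 = 75%, out | 4/4 = 100%, kept |
| Days 7, 14 (the only entries labelled visits) | 0/2 = 0%, out | 1/2 = 50%, out | 2/2 = 100%, kept |
| 6 hours plus Days 1, 2, 7, 14 | 3/5 = 60%, out | 4/5 = 80%, kept | 5/5 = 100%, kept |

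So Day 2 removals go on three of three counts and Day 7 removals on two of three.

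The Month 12 survey is labelled post-trial, so I leave it out. Including it changes the result by count. For a Day 14 removal without the survey, Days 1, 2, 7, 14 and Month 12 gives 4/5 = 80% (kept), while Days 7, 14 and Month 12 gives 2/3 = 67% (out).

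**Step 3: if B fails.** Suppose a patient removed on Day 2 still attends Days 7 and 14 and those visits count. The shares are then 4/4, 2/2 and 5/5, and nobody is lost.

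**Step 4: is there a Day 2 liver test?** Protection against Risks says: "Liver function tests, including serum transaminase and bilirubin, will be obtained on Day 2, Day 7, and Day 14". The Methods text and the Study Time Points table give only Days 7 and 14. If no Day 2 sample is drawn, only Day 7 liver cases are at risk, along with discretionary removals for adverse events.

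**Step 5: illustration.** All event counts are assumed, A and B hold, and there are 50 per arm. Take 6 CBD and 3 placebo cases, spread evenly over Days 2, 7 and 14.
- All treated: 6/50 = 12.0% vs 3/50 = 6.0%; difference 6.0 points, ratio 2.0.
- Day 2 and Day 7 cases dropped: 2/46 = 4.3% vs 1/48 = 2.1%; difference 2.3 points, ratio 2.1.
- Only Day 2 cases dropped (the 4/5 count): 4/48 = 8.3% vs 2/49 = 4.1%; difference 4.3 points, ratio 2.0.
- No Day 2 test, with 4 vs 2 cases split over Days 7 and 14: 4/50 = 8.0% vs 2/50 = 4.0% becomes 2/48 = 4.2% vs 1/49 = 2.0%, or is unchanged on the 4/5 count.
- Timing differs by arm, with Day 2 and Day 7 cases dropped: CBD even and placebo all on Day 14 gives 2/46 vs 3/50, ratio 0.7. CBD all on Day 14 and placebo even gives 6/50 vs 1/48, ratio 5.8.

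If all cases arise on Day 14, none is lost; if all arise on Day 2, all are lost. Absolute rates fall whenever early cases are dropped. The ratio hardly moves when timing is alike in both arms and can move either way when it is not.

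**The case against.** The strongest reply has four parts.

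*The term may not cover these events.* The withdrawal criteria list complication and adverse event as separate items, and nothing in the documents calls a raised liver test a complication. This stands, and it is why the point is conditional. If the term means intra-operative events only, the rule does not touch post-operative harms.

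*Removed patients may still be seen.* Days 7 and 14 are standard-of-care visits, and adverse event follow-up continues after participation. This also stands. But the plan does not say that such attendance counts towards the 80%.

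*The events are not lost.* An abnormal result that leads to withdrawal is an adverse event under Adverse Event Reporting, and liver tests and adverse events are reviewed quarterly. This is correct. A reader might infer that the plan conceals liver harm; the documents do not support that. What is at risk is the between-arm comparison, which neither the records nor the quarterly review is described as providing.

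*Some by-arm analysis of harm exists.* A reader might infer that, if complication rates is intra-operative only, no adverse event is compared by arm. That goes too far. Nausea incidence is a secondary objective compared between cohorts, and nausea that develops in the study meets the protocol's own definition of an adverse event. The absence of a by-arm table for liver tests and other adverse events would be missing detail, not in itself an error.

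**Conclusion.** The concern holds in conditional form. The plan states an exclusion rule that covers complication rates without a safety exception, alongside rules that remove patients because of harm. Under assumptions A and B, Day 2 removals leave the comparison on every in-study count examined, and Day 7 removals on two of three.

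Three stronger readings are not supported:
- That harm cases *will* be dropped: this needs A, B and a particular visit count together.
- That the rule makes CBD look safer by a known amount: no event rate is given, the 12% vs 6% illustration is not a forecast (hepatic toxicity is listed as rare), and the ratio can move in either direction.
- That Day 7 cases go on nearly every count, or that Day 14 cases are always safe: both depend on whether the post-trial survey is counted, and how.

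The change is still worth making. Which patients a harm comparison includes should not depend on the harm, and the remedy is nearly free.

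**What to change.** Add to Analysis of the Secondary Endpoint(s):

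'The 80% visit rule does not apply to complications, adverse events or liver tests. These are summarised descriptively by treatment received, in all randomised patients who took at least one ODT, and any event or value that led to removal is counted. Adverse events follow the definition under Adverse Event Reporting. Intra-operative complications are reported separately.'

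The definition has to be named because the Data and Safety Monitoring Plan describes adverse events as reactions to CBD, which a placebo patient cannot have. The table should also state how many patients had no post-baseline liver test. The removal rules and the efficacy analysis do not change.

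The cost is one paragraph and one table from data already collected, with no new visits. The downside is imprecision at 50 per arm. By the Clopper-Pearson method, 0/50 has an upper 95% limit of 7.1% and 6/50 an interval of 4.5% to 24.3%; 6/50 vs 3/50 gives Fisher p = 0.49. The table cannot establish liver safety and should be labelled descriptive. The adverse event definition is broad, so expected post-operative symptoms may make any-event counts high in both arms.

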The Endocannabinoid System (ECS) is a neuromodulatory system that has recently emerged as a promising new therapeutic target with many potential applications. The ECS is comprised of the CB1 and CB2 cannabinoid receptors, endogenous cannabinoid ligands known as Endocannabinoids, and the enzymes responsible for the synthesis and degradation of cannabinoids. The ECS is involved in regulating the inflammatory response to injury, as well as modulating pain and thus is a pharmacological target in pain management.

Cannabidiol (CBD) has become a subject of growing interest since Congress passed the 2018 Farm Bill, which legalized Industrial Hemp (*Cannabis Sativa* plants containing <0.3% THC content) and its derivative cannabinoids, including CBD. CBD is a non-psychotropic cannabinoid that has been reported to exhibit a range of therapeutic properties. It is well tolerated in humans with a low risk of side effects, and has not been shown to interact with, nor potentiate the effects of opioid analgesics. This makes it an attractive target for managing post-operative pain.

However, CBD suffers from poor oral bioavailability (6-11%) due to extensive first pass metabolism via CYP3A4. To mitigate this issue, CBD will be administered in a proprietary Orally Disintegrating Tablet (ODT) provided by Concours Pharmaceuticals®. This formulation allows for transmucosal absorption of CBD via the buccal mucosa in the oral cavity. This delivery method reduces the effective dose of CBD needed to achieve relevant plasma concentrations.

Given the potential risks treating postoperative pain with prolonged opioid use, we are proposing a study to evaluate the effects of CBD as an adjunct to opioid analgesics. Therefore, the purpose of the proposed study is to evaluate the analgesic effects of CBD administered via this ODT to patients that have undergone shoulder arthroscopy, with the goals of reducing post-operative pain and lessening the need for prolonged opioid therapy. Our hypothesis is that CBD will reduce postoperative pain, opioid use and associated side effects like nausea.

Study Design

This will be a multi-center, double-blinded randomized controlled study. The study is comparing postoperative pain, patient satisfaction, and opioid use in two cohorts: patients undergoing

The use of cannabidiol (CBD) in pain reduction and opioid use after shoulder arthroscopy. A Double-Blind, Randomized Control Study

Version 06/28/2022

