| Day 0 - Day of Surgery | Baseline suicidality assessment (C-SSRS), Record Pain (6hrs and 24 hrs), Record clinical data during surgery and post op including time to discharge from PACU and time to discharge from the hospital, monitor for AEs |
| Day 1 | Record Pain, Opioid consumption, CBD consumption, Satisfaction, monitor for AEs |

The use of cannabidiol (CBD) in pain reduction and opioid use after shoulder arthroscopy. A Double-Blind, Randomized Control Study

Version 06/28/2022

| | |
|-----------------------------------|--|
| Day 2 | Record Pain, Opioid consumption, CBD consumption, Satisfaction, Nausea, monitor for AEs |
| Day 7 - Standard of Care Visit 1 | Record Pain, Opioid consumption, CBD consumption, Satisfaction, Nausea, Liver Function Tests - Non-standard of care, C-SSRS, Drug accountability, monitor for AEs |
| Day 14 - Standard of Care Visit 2 | Record Pain, Opioid consumption, CBD consumption, Satisfaction, Nausea, monitor for AEs Liver Function Tests - Non-standard of care, C-SSRS, Drug accountability and review of completed subject diary, monitor for AEs |
| Month 12 – Post-Trial Survey | Record Pain; Complete ASES, KJOC Shoulder, and SANE assessment |

Data Analysis and Statistical Plan

Our power analysis was based on the literature of post-operative pain control following shoulder arthroscopy. Under the assumption of a VAS of 3 and 1.8 for the control and CBD respectively, with a SD of 2: Group sample sizes of 45 in each group would achieve 80% power to reject the null hypothesis of equal means when the population mean difference between Control and CBD is $\mu_1 - \mu_2 = 3.0 - 1.8 = 1.2$ with a standard deviation for both groups of 2.0 at a significance level (alpha) of 0.05 using a two-sided two-sample equal-variance t-test. Thus, to allow for a 5% drop-out at 14-day follow-up, 100 patients would be required to enroll.

For descriptive statistics, categorical values will be described by percentages, and continuous variables will be described by means with standard deviations. To compare primary and secondary outcomes, a T-Test will be performed, with a p-value of 0.05 set to determine statistical significance. Testing will be performed to determine whether sample distribution is normal; if not, non-parametric testing will be performed.

Analysis of the Primary Efficacy Endpoint(s)

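### Secondary outcomes are each tested at an unadjusted 0.05 with no key secondary, testing order, alpha split or exploratory label, although opioid use and nausea are part of the stated hypothesis

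*Combined protocol and SAP*

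**What the plan says.** The general rule, in Data Analysis and Statistical Plan, treats primary and secondary outcomes alike: "To compare primary and secondary outcomes, a T-Test will be performed, with a p-value of 0.05 set to determine statistical significance". Analysis of the Secondary Endpoint(s) repeats the threshold: "a T-Test will be performed, with a p-value of 0.05 set to determine statistical significance. For categorical variables, a Fisher's exact test will be performed". That section's own list is short: "To compare secondary outcomes (opioid use, satisfaction), complication rates".

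The Secondary Objective is wider. It asks about "differences in patient satisfaction, the incidence of opioid induced nausea, and the numbers of opioids and CBD/placebo ODTs consumed by the two patient cohorts". Nausea and the ODT count therefore enter the tested set through the objective and the general rule, not through the secondary analysis section.

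The Rationale gives two of these outcomes the standing of hypotheses: "Our hypothesis is that CBD will reduce postoperative pain, opioid use and associated side effects like nausea". Opioid use is also in the trial title.

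Methods and Procedures sets the recording times. Opioid use has four: "Percocet consumption will be recorded at 24 hours, 2 days and 7 days, and 14 days after surgery". Satisfaction has four: "Patients will record their satisfaction with their management, on a 0-10 scale, 24 hours, 2 days and 7 days, and 14 days after surgery". Nausea has three (Days 2, 7 and 14). No section says which time, or which summary over time, is the one to be compared. No section ranks the secondary outcomes, divides alpha, makes them conditional on the pain result or calls them exploratory.

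**The concern.** A threshold that decides statistical significance, applied separately to each of several outcomes, permits a claim from any of them. That is tolerable for outcomes understood to be supportive. Here opioid use and nausea are part of what the trial sets out to show, and nothing in the plan separates a confirmatory opioid result from an incidental one. Because the time of analysis is also open, the analyst could test every recorded time, or choose one after seeing the data, and still be within the plan.

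At stake is how the opioid and nausea results may be reported. As written, a nominal p below 0.05 on one secondary comparison could be called significant whatever the pain comparison showed, and the reader could not tell how many comparisons had been open to the same claim.

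**Working it through.** **The plan's own figure.** The documents state no family-wise error rate and no count of secondary tests. Their one error-rate calculation is the sample size: difference 1.2, SD 2.0, two-sided alpha 0.05, 80% power. The exact t-test gives 44.6, rounded up to 45 per group, with 80.4% power, so the stated 45 is reproduced. That calculation covers a single pain comparison.

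**Inputs from the documents.**
- Threshold per test: 0.05. The power calculation is two-sided, and I take the secondary tests as two-sided too.
- Scheduled times: opioid use 4, satisfaction 4, nausea 3.
- Outcomes if each is tested once: opioid use and nausea (2); with satisfaction (3); with ODT count and complication rates (5).

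**Assumptions.** The number of tests actually run and the correlations between them are not given. I take all nulls as true and the test statistics as normal, with correlation from 0.8 down to 0.

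**Formulas.** For k independent tests, the chance of at least one rejection is 1 − 0.95^k. For common correlation r, it is 1 − P(all |Z| < 1.96), by numerical integration. The Bonferroni upper bound is 0.05k, whatever the correlation.

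| Family | k | Independent | r = 0.5 | r = 0.8 | Bound |
|---|---|---|---|---|---|
| Opioid, nausea, once each | 2 | 1 − 0.95^2 = 9.8% | 9.1% | 7.8% | 10% |
| Three outcomes, once each | 3 | 1 − 0.95^3 = 14.3% | 12.5% | 9.8% | 15% |
| Five outcomes, once each | 5 | 1 − 0.95^5 = 22.6% | 18.3% | 12.7% | 25% |
| Opioid (4) + nausea (3), every time | 7 | 1 − 0.95^7 = 30.2% | 23.0% | 14.9% | 35% |
| Opioid (4) + satisfaction (4) + nausea (3), every time | 11 | 1 − 0.95^11 = 43.1% | 30.4% | 18.0% | 55% |

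**A more realistic correlation pattern.** Repeated measures of one outcome should correlate more strongly than different outcomes do. Simulation with 400,000 draws gives:

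| Within / between outcomes | 7 tests | 11 tests |
|---|---|---|
| 0.5 / 0.2 | 25.6% | 36.4% |
| 0.5 / 0.3 | 24.9% | 34.8% |
| 0.8 / 0.3 | 19.5% | 27.6% |
| 0.8 / 0.5 | 18.3% | 24.9% |

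**Direction.** These rates count rejections favouring either arm. Counting only those favouring CBD (2.5% per test), the same four settings give about 9-13% for 7 tests and 12-19% for 11, roughly half.

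**After the change.** One key secondary at 0.05 has a 5% error rate. Holm across two outcomes holds the family at or below 5%. As a check on its first step, two independent tests at 0.025 each give 1 − 0.975^2 = 4.94%. The exploratory label does not lower the chance of a nominal p below 0.05 among the remaining outcomes; it removes the claim that would rest on it.

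**The case against.** The strongest reply is that no section says every recorded time will be tested. Methods and Procedures says when data are collected, and the analysis section speaks of a t-test in the singular. The Secondary Objective refers to "patient satisfaction, the incidence of opioid induced nausea, and the numbers of opioids and CBD/placebo ODTs consumed by the two patient cohorts", which can be read as one nausea incidence and one count each of opioids and ODTs. This stands. The 7- and 11-test figures show what the plan permits, not what it commits to, and the one-test-per-outcome figures must be given beside them.

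A reader might infer that the opioid and nausea claims themselves carry a 25-36% false-positive chance. The documents do not support that. The range belongs to 11 tests including satisfaction; opioid use and nausea make seven tests, whose rate cannot exceed 35% and is 18-26% under the same correlations. Nor is it the error rate of any one claim: each test taken alone stays at 5%.

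It is also fair to say that these outcomes are labelled secondary and that only pain is powered. That limits how serious the point is. It does not remove it, because the plan sets a significance threshold for these outcomes and places two of them in the hypothesis.

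Finally, making opioid use conditional on a significant pain result is not the only sound design. Percocet is taken as needed, so lower opioid use with similar pain scores is a plausible form of benefit, and a strict gate would bar that claim. This stands too: the gate is the sponsor's choice.

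**Conclusion.** The point holds as a gap in error control for the secondary outcomes and in the definition of what is tested. On the most sparing reading, opioid use and nausea tested once each, the family-wise rate is about 8-10%, already well above 5%. For three to five outcomes tested once each it is 10-23%. The higher figures, 15-30% for opioid use plus nausea and 18-43% with satisfaction added, apply only if every scheduled time is tested. All of these rest on assumed test counts, assumed correlations and all nulls being true. Because the rates are two-sided, the chance of a false finding in favour of CBD is about half as large. This is an inexpensive improvement to make before analysis; it is not a flaw that undermines the primary comparison.

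**What to change.** In Analysis of the Secondary Endpoint(s), replace the blanket 0.05 rule with wording such as: the key secondary endpoint is the total number of Percocet tablets taken through Day 14, tested two-sided at 0.05; all other secondary comparisons, including opioid use at individual times, are exploratory, are reported as estimates with 95% confidence intervals and are not described as statistically significant.

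If a confirmatory nausea claim is also wanted, prespecify one nausea summary and apply Holm across it and the Percocet total: the smaller p-value against 0.025 and, if that passes, the larger against 0.05. Bring the general rule in Data Analysis and Statistical Plan into line.

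Testing the key secondary only after a significant pain result is optional. It would first need one prespecified primary VAS comparison, because the plan defines the primary outcome only as the VAS score, and that is recorded at five times within 14 days.

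The cost is wording in the protocol and SAP; no new data, patients or visits are needed. The downside is that a nominal p below 0.05 on an exploratory secondary can no longer be reported as significant.
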